**Table 3. Dosing schedule and safety precautions**

	Dose	Frequency	Safety precautions
Day 1	100 mg	Twice daily	Subjects will take first dose of medication at study site, in front of study personnel.
Day 2	100 mg	3x daily	
Day 3	100 mg	3x daily	
Day 4	200 mg	3x daily	Subjects will be called and assessed for medication side effects/tolerability.
Day 5	200 mg	3x daily	
Day 6	200 mg	3x daily	
Day 7	200 mg	2x daily	LFTs repeated on Day 7 or 8 (after last dose of medication).

#### 4) Test procedures

**a) Pre-treatment scan session (day 1).** Upon their arrival at the MRI suite, subjects give a breath or saliva sample for alcohol testing, to ensure they have not recently consumed alcohol, and administered the Clinical Institute Withdrawal Assessment for Alcohol-Revised (CIWA-Ar; 65), to ensure they are not currently experiencing significant alcohol withdrawal symptoms. Subjects with a breath or saliva alcohol content  $> 0.02$  will be rescheduled, and those with a CIWA-Ar score  $> 3$  will not be scanned. However, in our experience, very few subjects arrive intoxicated or in alcohol withdrawal. Subjects will then be administered the Vocabulary and Matrix Reasoning subtests of the Wechsler Abbreviated Scale of Intelligence-II (WASI-II). For subjects who were referred from study 46264 (PI: [name]), the WASI-II score from that study will be used, since this assessment cannot be repeated over short intervals. Scans will be performed with a Siemens 3.0T TIM Trio MR scanner with actively shielded magnet and high-performance gradients (45 mT/m, 200 T/m-sec). Each scan will last approximately 60 minutes and will consist of a high-resolution anatomical image, for subsequent stereotactic registration, and two gradient-echo echoplanar imaging (EPI) sequences: 1) an alcohol cue-reactivity task; and 2) three runs of a response inhibition task. [name] will supervise all aspects of the proposed neuroimaging procedures, which are similar to those used in our current ARC project. Following the scan, blood will be collected for the red blood cell COMT activity assay. Subjects will then be randomized to tolcapone or placebo medication, and will take their first dose of medication at the study site.

[figure not shown]
**1. Alcohol cue-reactivity task.** This task, for which detailed methods are described in our past papers (e.g., 66; 67), reliably elicits OFC and vmPFC activation (68). Subjects are given a sip (10 mL) of 80-proof liquor mixed with juice (1:3 ratio), and are then shown pseudorandomly interspersed images of alcoholic (ALC) and non-alcoholic (BEV) beverages, visual control images, and fixation (see **Figure 5**). These stimuli were selected from a normative set, supplemented with images from advertisements, and matched by color, hue, and complexity. Stimuli are presented in six 120-s epochs, each consisting of four 24-s blocks of an image type (one block each of ALC, BEV, control, and fixation). Each block is followed by a 6-s washout period, allowing the hemodynamic response from the previous block to decline before the next is presented. A 12-m gradient-echo EPI sequence will be acquired (parameters: repetition/echo time (TR/TE)= 2200/35 ms; flip angle (FA)= 90°; field of view (FOV)= 192 mm^2; voxel size= 3.75 x 3.75 mm; 36 contiguous 3-mm-thick slices).

**Figure 5.** Sample alcohol (left) and beverage (right) images from the cue-reactivity task.

**2. Response inhibition task.** This task is adapted from a well-validated event-related stop-signal task (38) that reliably elicits dmPFC, dlPFC, and inferior frontal gyrus activation. We have used this task during the current ARC funding period. Subjects are presented with a series of trials on which they are instructed to respond as quickly as possible to a target stimulus (open circle). On 25% of trials, the target stimulus is followed by a “stop” stimulus (X: the “stop signal”), and subjects are instructed to attempt to withhold their responses on these trials (see **Figure 6**).

**6).** The onset latency between the appearance of the target and the stop signal begins at 189 ms and increases by 67 ms (i.e., becomes more difficult) if the subject is able to withhold his or her response to that trial; conversely, onset latency decreases by the same amount if the subject fails to inhibit his or her response. This “psychophysiological staircase” procedure (69) ensures that all subjects perform the task equivalently, thereby removing behavioral variance and allowing isolation of the neural substrates of response inhibition. Responses must be made within 1 s of stimulus presentation, and the inter-trial interval varies randomly between 1 and 4 s, allowing subjects to develop a prepotent “go” response to the more frequent targets that are not followed by stop signals, but preventing rhythmicity in responding. To ensure a sufficient number of the less frequent stop trials, three 10-m gradient-echo EPI runs of the task will be acquired (parameters: TR/TE= 2000/25 ms; FA= 85°; FOV= 220 x 220 mm; voxel size = 3.44 x 3.44 mm; 32 contiguous 4-mm-thick slices).

**Figure 6.** Target stimulus (left) and stop signal (right) from the response inhibition task.

**b) Natural drinking period (days 1-6).** Subjects will be given no specific instructions regarding their drinking during the first six days of study medication ingestion. On day 7, before the scan, subjects will report their drinking over the previous six days using the Timeline Follow-back calendar method (70).

**c) Post-treatment scan session (day 7).** Subjects will again give a breath or saliva sample for alcohol testing and assessed for alcohol withdrawal symptoms, and the functional sequences acquired during the pre-treatment scan will be repeated. At this visit or the following day (day 8), blood for LFTs and the COMT activity assay will also be collected.

**d) Feedback session (day 8) and follow-up.** The day after the second brain scan, subjects will be seen by a clinician for a 1-hour motivational enhancement session, using information from the GSC brief treatment, to motivate them to seek treatment for any problems related to their drinking. To ensure participation, subjects will not be compensated for study participation until after this session. If subjects express interest in treatment, one additional session will be offered. Subjects will also be shown the NIAAA “Rethinking Drinking” website. The Physical Symptom Checklist will be repeated at this time. If any major physical complaints are noted, the subject will be invited to return to the laboratory for an in-person evaluation by a study physician.

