### B. RESEARCH DESIGN AND METHODS

#### 1) Timeline and general design of the study

Enrollment and data collection will be conducted during years 1-4 and the first half of year 5; the study blind will be broken in the second half of year 5, and data analysis will begin at that point. Ninety non-treatment-seeking subjects (20 per year in years 1-4, and 10 in year 5) with *DSM-5* Alcohol Use Disorder (AUD) will be randomized, on the basis of their *COMT* genotype, to tolcapone (titrated to 200 mg, 3x/day) or placebo for seven days, and will complete the procedures detailed in **Table 2**. Immediately prior to randomization (day 1), subjects will undergo a pre-treatment fMRI scan, during which anatomical, alcohol cue-reactivity, and stop-signal scans will be acquired. If more than one week has passed between a subject's initial assessment by the ARC Clinical

Intake and Assessment Core, urine drug screening and pregnancy testing will be repeated, as will measures of recent alcohol consumption (e.g., Timeline Follow-back and Obsessive Compulsive Drinking Scale). On study day 7, subjects' drinking over the previous six days will be assessed, and the fMRI procedures will be repeated. Blood will be drawn on days 1 and 7 to assess tolcapone effects on COMT activity in red blood cells. On day 8, subjects will be counseled regarding alcohol problems and encouraged to participate in treatment if indicated. Subjects will be compensated \$300.

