**Table 2. Study visits and procedures**

Visit	Procedure
Day 1	Pre-treatment scan, blood draw, and medication randomization. After the scan, subjects will receive a blister-pack containing study medication and will take the first dose at the study site in front of study personnel.
Day 7	Post-treatment scan and blood draw. Before the scan, drinking over the previous six days will be assessed. LFTs will be repeated on this day or the following day, after medication administration is complete.
Day 8	Feedback session. Subjects will receive motivational enhancement counseling related to their drinking.

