**c) Dosing.** Subjects will be instructed to take medication capsules (each containing either placebo or 100 or 200 mg of tolcapone) in the morning, at noon, and in the evening on the schedule shown in **Table 3**. On day 7, subjects will take their final dose between 11 am and 2 pm, at least one hour before the final brain scan.

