**2. COMT activity assay.** As part of this aim, we will also measure COMT inhibition peripherally, in red blood cells (since it is not possible to measure it in the brain), both to confirm that *COMT* val158met genotype indeed affects this construct among individuals with AUD and to evaluate medication adherence and/or individual variation in response to tolcapone. A previously described COMT activity assay (29) will be conducted in the CNL, and the GLM will be used to analyze effects of *COMT* genotype, medication, and their interaction on change in COMT activity between days 1 and 7. We will also evaluate whether, in the tolcapone group, level of COMT

inhibition is associated with amount of drinking in the natural environment, and will consider using this variable as a covariate in other analyses if it varies significantly between subjects.

**e) Aim 2: Test tolcapone and *COMT* val158met effects on cortical activation related to alcohol cue reactivity and cognitive control, and evaluate whether these actions mediate its effects on drinking.**

**1. Preprocessing:** Functional images from the cue and stop-signal tasks will be pre-processed with the FSL software package (FMRIB Analysis Group, Oxford, UK) (85); steps will include realignment to the first volume, smoothing with an anisotropic 8-mm FWHM kernel, high-pass filtering, resampling to 2-mm isotropic voxels, and stereotactic registration to the Montreal Neurological Institute 152-subject average template. Subjects with > 2 mm translational/2° rotational movement during either task will be excluded from analysis.

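### The test procedures allow the COMT-activity blood sample on day 7 or day 8, while the design, the visit table and the analysis place it on day 7

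*Combined protocol and SAP*

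**What the plan says.** The combined protocol and SAP gives the timing of the post-treatment COMT sample in four places.

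- B.4 c), Post-treatment scan session: "At this visit or the following day (day 8), blood for LFTs and the COMT activity assay will also be collected".
- B.1, Timeline and general design: "Blood will be drawn on days 1 and 7 to assess tolcapone effects on COMT activity in red blood cells".
- Table 2, day 7 row: "Post-treatment scan and blood draw". The same row gives a two-day option, but for the liver tests: "LFTs will be repeated on this day or the following day, after medication administration is complete".
- B.5 d) 2, COMT activity assay: the modelled outcome is the "change in COMT activity between days 1 and 7".

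B.3 a), Table 3 and C.2 b) item 4 also mention a day 7 or 8 window, in each case for liver tests only.

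On dosing, B.3 c) says: "On day 7, subjects will take their final dose between 11 am and 2 pm, at least one hour before the final brain scan". The rationale for tolcapone in section A describes the drug as a reversible inhibitor. B.5 d) 2 plans no adjustment for the day of the draw or the time since the last dose.

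**The concern.** The two blood tests have opposite needs. The liver tests are meant to follow the end of dosing, so a one-day window does them no harm. The COMT assay is meant to show what the drug does to the enzyme, so it belongs on the dosing day. B.4 c) puts both under one window.

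If sites follow B.4 c), some subjects are sampled on the day of the last dose and others the day after, and all are analysed as day 7. B.5 d) 2 gives the assay several jobs: to confirm that genotype and drug affect COMT activity, to help judge adherence and individual response, and to relate inhibition to drinking within the tolcapone group. Inhibition is also to be considered as a covariate elsewhere if it differs enough between subjects. If inhibition falls between the two days, part of that difference would come from scheduling.

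**Working it through.** The plan gives no figure to reproduce. The check compares the passages, works out the clock times, and illustrates the effect of mixing draw days.

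**1. Passages side by side**

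| Place | COMT sample | Liver tests |
|---|---|---|
| B.1 | day 7 | not stated |
| Table 2 | day 7 (blood draw) | day 7 or 8 |
| B.5 d) 2 | day 7 | not stated |
| B.3 a), Table 3, C.2 b) item 4 | not stated | day 7 or 8 |
| B.4 c) | day 7 or 8 | day 7 or 8 |

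Only B.4 c) extends the window to the COMT sample.

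**2. Time from last dose to a day 8 draw**

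Input from the plan: last dose between 11:00 and 14:00 on day 7. Section B.4 d) puts the feedback session on the day after the scan but gives no clock time, so the day 8 draw hours are an assumption.

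Shortest gap = 24 + earliest draw hour − 14. Longest gap = 24 + latest draw hour − 11.

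- Draws 08:00 to 17:00: 24 + 8 − 14 = 18 h; 24 + 17 − 11 = 30 h.
- Draws 09:00 to 14:00: 24 + 9 − 14 = 19 h; 24 + 14 − 11 = 27 h.
- Draws 09:00 to 12:00: 24 + 9 − 14 = 19 h; 24 + 12 − 11 = 25 h.

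The documents therefore support a gap of about one day and nothing more exact.

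**3. Time from last dose to a day 7 draw**

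On day 1 the blood is taken after the scan (B.4 a)). If day 7 follows the same order, the draw comes at least about 1 h + 1 h = 2 h after the dose: at least one hour before the scan, plus a scan of about 60 minutes. The plan does not state the order for day 7.

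**4. Effect of mixing draw days (illustration)**

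Let f be the share of tolcapone subjects drawn on day 8, and r the share of day 7 inhibition still present then. Both are assumptions. Set day 7 inhibition to 1 for every subject.

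- Mean measured inhibition = 1 − f(1 − r).
- SD caused by draw day alone = √(f(1 − f)) × (1 − r).

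| r | Mean, f = 0.25 | SD, f = 0.25 | Mean, f = 0.5 | SD, f = 0.5 |
|---|---|---|---|---|
| 0 | 75% | 43% | 50% | 50% |
| 0.25 | 81% | 33% | 62.5% | 37.5% |
| 0.5 | 87.5% | 22% | 75% | 25% |
| 0.75 | 94% | 11% | 87.5% | 12.5% |
| 1 | 100% | 0% | 100% | 0% |

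All entries are percentages of the day 7 inhibition. For example, with f = 0.25 and r = 0.5 the mean is 1 − 0.25 × 0.5 = 0.875. The effect vanishes only if inhibition is undiminished a day later (r = 1) or nobody is drawn on day 8 (f = 0).

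**The case against.** The strongest reply is that this is loose wording in one sentence. The general design, the visit table and the analysis variable agree on day 7, the likeliest intention is that only the liver tests have a window, and nothing shows that any COMT sample was to be taken on day 8. That is fair as to intention. But B.4 c) is the section that tells staff what to do at the visit, and it permits a day 8 draw.

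A reader might infer from the word reversible that the effect has largely gone by day 8. The documents do not support this. Reversible describes the kind of inhibition, not how long it lasts, and the plan gives no half-life, no duration of red-cell inhibition and no time course. Any stated percentage loss rests on an assumed decay rate.

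A reader might also infer that subjects drawn on day 8 would be classed as non-adherent. The plan does not go that far. It gives no adherence cut-off for COMT activity, and adherence has its own measure, urinary riboflavin on day 7, with its own threshold (B.3 b)). Nor does the plan link draw day to arm or genotype, so the expected harm is dilution and added noise, not a directional bias between genotypes.

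**Conclusion.** The contradiction stands and should be resolved. Followed as written, B.4 c) would mix samples from the dosing day with samples taken off drug about one day later, under an analysis that treats them alike. If inhibition has declined by then, measured inhibition is diluted, and scheduling variation enters both the individual-response analysis and the inhibition-drinking association. It could also sway the decision on using inhibition as a covariate.

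The size cannot be computed from the documents, because the share drawn on day 8 and the inhibition remaining are both unknown. The tables above show a range, not an estimate. The assay is a secondary part of Aim 1. The primary outcome, drinks per day on days 1 to 6, is affected only through the covariate route, which the plan says it will consider and does not commit to.

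**What to change.** Split the sentence in B.4 c) so that it agrees with B.1, Table 2 and B.5 d) 2:

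- Draw the COMT-activity sample on day 7, after the final dose, for every subject (for example after the scan, as on day 1).
- Record the draw time and the time since the last dose.
- Leave the day 7 or 8 window in place for the liver tests only.

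B.3 a) reports over 70 subjects already enrolled, so some COMT samples may already have been taken on day 8. For any such samples, report the draw day by arm, and either analyse them separately or add a draw-time by medication term to the COMT-activity model. A single time term common to both arms would not fit, because the placebo arm has no drug inhibition to lose. If all draws are on day 7, no such term is needed.

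The cost is one sentence of text. Subjects already attend on day 7, and Table 2 already lists a blood draw that day. The downside is that subjects whose liver tests are left to day 8 would have two draws instead of one.

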## 5) Data collection and analysis

[figure not shown]
### a) Data collection and management

Self-report measures will be collected with the Research Electronic Data Capture (REDCap) system (<http://project-redcap.org>), implemented on a password-protected Apple iPad. REDCap is a mature, secure web application for building and managing online surveys and databases. Because no keystroke data entry is necessary, REDCap reduces the risk of data entry errors and saves staff time. Each subject will use the iPad to record answers to each questionnaire. In addition, the system reminds the subject to complete missing items before the next questionnaire is administered. Data collected using REDCap are automatically uploaded to a secure, password-protected online database, and can subsequently be exported into SPSS data files for analysis. Studies using REDCap for data collection in clinical research have been approved by MUSC's IRB, and the study PI has successfully implemented it in other research projects at MUSC.

Data storage and management for MRI data will be handled by the Center for Biomedical Imaging (CBI). A significant component of CBI is the informatics management system, which consists of an integrated system of Linux workstations surrounding a central core of Linux servers and a growing cluster facility, allowing network access for data retrieval and image analysis both locally and to CBI faculty working remotely. A full-time informatics person manages the system, providing system design, trouble-shooting, data export, software maintenance, and systematic backup. The system is stored at MUSC and is password-protected and encrypted for data integrity and confidentiality.

**b) Sample size determination and power analysis.** The effect size for APZ among *COMT* met-allele homozygotes in our preliminary data ( $d = 1.7$ ) and the genotype frequencies for the *COMT* val158met SNP were used to determine sample size and statistical power for Aim 1. Power was calculated iteratively with repeated estimation from the SPSS (IBM, Armonk, NY) MANOVA package. This analysis indicated that power to detect a *COMT* by tolcapone interaction in which tolcapone's effect size among val-allele homozygotes is 1.3 or greater is 0.8 with 30 subjects per genotype group. We anticipate that, out of 140 subjects with normal liver enzymes referred by the **ARC Clinical Intake and Assessment Core**, approximately 31 will carry the met/met genotype, 65 the val/met genotype, and 44 the val/val genotype. Accordingly, val/met and val/val subjects will be chosen for inclusion in this project or the other clinical project on the basis of an *a priori* randomization table. Those not chosen for inclusion will be referred to Project 4.

For Aim 2, the path coefficients  $a$ ,  $b$ , and  $c'$  will be used to estimate the strength of the causal relationship between each pair of variables (see **Figure 7**), and mediation will be determined by the significance of the joint ( $a * b$ ) product: does the indirect path from the independent variables through the mediator to the dependent variable (drinking) explain significant variance? Fritz and MacKinnon (80) have conducted large-scale simulation to form empirical estimates of power for mediated effects similar to Cohen's (81) original analysis of effect size for simpler regression problems. For 90 subjects and medium effect sizes ( $d = 0.5$ ) for the two arms of the indirect effect, power to detect a mediated effect is 0.8. Thus, power analyses for both Aims 1 and 2 suggest that a total  $N$  of 90 will yield  $\geq 0.8$  power to detect the hypothesized effects.

**Figure 7.** Proposed mediation pathway. The product ( $a * b$ ) estimates how much of the effects of *COMT* genotype and tolcapone on bar-lab drinking are due to cortical activation to the cue or stop-signal tasks.

**c) Randomization plan.** *COMT* genotype will be used to prospectively randomize subjects to tolcapone or placebo medication. The *COMT* val/val genotype is more frequent among African-Americans (AA) than among European-Americans (EA), the two primary racial groups in the Charleston, SC area. In our preliminary data, 16% of subjects were AA and 83% were EA, consistent with the usual racial distribution of our studies. Val/val genotype frequency was 0.70 among AA and 0.25 among EA, consistent with dbSNP allele frequency estimates (Asian-Americans, who have comprised ~5% of our past study populations, have val/val frequencies similar to AA). To account for racial differences in val-allele frequency, we will stratify subjects by race (AA/Asian vs. EA) and *COMT* genotype (val/val, val/met, or met/met), and will then urn randomize subjects to tolcapone or placebo. Since some recent data suggest that the effects of both tolcapone (82) and *COMT* variation (83; 84) differ by sex, sex will be used as the urn variable within each of these six strata. The **ARC Biostatistics Core** statistician will oversee this process.

**d) Aim 1: Evaluate tolcapone and *COMT* val158met effects on drinking in the natural environment during six days of treatment.**

**1. Analysis and expected results.** Analyses for all aims will be conducted with consultation from the **ARC Biostatistics Core** statistician. The main dependent variable for Aim 1 will be drinking under natural conditions during days 1-6 (drinks per day). The general linear model (GLM) will be used to analyze the main effects of tolcapone and *COMT* genotype, as well as their interaction, on this variable. Pre-treatment drinking will be included as a covariate in these models, as will any salient demographic variables (e.g., age, cigarette smoking, family history of alcoholism). We predict that tolcapone, relative to placebo, will reduce natural drinking, and will do so to a greater extent among *COMT* val-allele homozygotes.

**2. COMT activity assay.** As part of this aim, we will also measure COMT inhibition peripherally, in red blood cells (since it is not possible to measure it in the brain), both to confirm that *COMT* val158met genotype indeed affects this construct among individuals with AUD and to evaluate medication adherence and/or individual variation in response to tolcapone. A previously described COMT activity assay (29) will be conducted in the CNL, and the GLM will be used to analyze effects of *COMT* genotype, medication, and their interaction on change in COMT activity between days 1 and 7. We will also evaluate whether, in the tolcapone group, level of COMT

inhibition is associated with amount of drinking in the natural environment, and will consider using this variable as a covariate in other analyses if it varies significantly between subjects.

**e) Aim 2: Test tolcapone and *COMT* val158met effects on cortical activation related to alcohol cue reactivity and cognitive control, and evaluate whether these actions mediate its effects on drinking.**

**1. Preprocessing:** Functional images from the cue and stop-signal tasks will be pre-processed with the FSL software package (FMRIB Analysis Group, Oxford, UK) (85); steps will include realignment to the first volume, smoothing with an anisotropic 8-mm FWHM kernel, high-pass filtering, resampling to 2-mm isotropic voxels, and stereotactic registration to the Montreal Neurological Institute 152-subject average template. Subjects with > 2 mm translational/2° rotational movement during either task will be excluded from analysis.

**2. Cue task analysis:** The averaged timecourse of the blood oxygen level dependent signal (BOLD) will be extracted from each subject's preprocessed images from *a priori* anatomically defined regions of interest (ROIs), defined as 6-mm-radius spheres around literature-based points in the vmPFC (BA 10) and OFC (BA 11). Hierarchical linear modeling (HLM v. 7.0, Scientific Software International, Skokie, IL) will then be used to calculate the difference in activation between the ALC and BEV blocks of these timecourses, and to analyze maximum likelihood estimates for ALC vs. BEV activation as a function of time, treatment, genotype, and the cross-level interactions of these factors. Specifically, the cue task stimuli will be nested within time (post- vs. pre-treatment scan); time will be nested within subject; and subjects will be nested within treatment (tolcapone vs. placebo) and *COMT* genotype (val/val vs. val/met vs. met/met).

**3. Stop-signal task analysis:** For each of the three task runs, trials will initially be classified as fixation, successful/unsuccessful hits (go trials), or successful/unsuccessful inhibitions (stop trials), and an event-related GLM, in which the hemodynamic response function (HRF) is convolved with the onset times of each trial, will be used to model each subject's preprocessed images with FSL FEAT v. 5.90. To eliminate effects of task-correlated motion, for each subject, the six motion parameters from the realignment will be also included in this GLM. For each subject, two contrast images will be generated for each run: 1) successful vs. unsuccessful inhibitions; and 2) go trials following unsuccessful inhibition trials on which the subject's reaction time increased vs. decreased, relative to the mean go trial reaction time (i.e., following an error, the subject's behavior became more vs. less restrained). The latter contrast, termed "post-error slowing", is an index of cognitive control (86). The three runs will be combined with a fixed-effects model, and a linear mixed effects model (FSL FLAME) will be used to test the interacting effects of time, treatment, and *COMT* genotype on both contrasts across the whole brain, with a voxelwise threshold of  $z > 2.3$  and a cluster threshold of  $p < .05$ , corrected for the false discovery rate. For each subject, individual percent-signal-change (PSC) values for each contrast will also be extracted from *a priori* anatomically defined ROIs, defined as 6-mm-radius spheres around literature-based points in dmPFC (BA 9) and bilateral dIPFC (BA 46) and IFG (BA 47).

**4. Expected mediation results:** We will test each of the vmPFC and OFC ALC vs. BEV coefficients and the dmPFC, dIPFC and IFG PSC values for the stop-signal contrasts (post- vs. pre-treatment) as individual mediators of the medication by genotype interaction on drinking (see **Figure 7**). To compare the effects of individual mediation by activation of any of the ROIs with the combined effects of cue-elicited and response-inhibition-related cortical activation, we will also test a multiple mediation model, in which the brain activation values described above are all tested in the same model. Using the SPSS AMOS package, we will model covariances between these ROI values (to partial out their shared variance), and will test whether the unique variance of the five ROIs collectively mediates the relationship between medication, genotype, and drinking to a greater extent than any individual ROI. To satisfy criteria for complete mediation, the medication and genotype variables must significantly predict the brain activation values, which must themselves predict significant variance in the drinking variables, and the medication by genotype interaction must be non-significant when the brain activation values are added to the model. If this interaction is still significant in the combined model, criteria for partial mediation can be satisfied if the indirect path between the interaction, the brain activation values, and drinking is also significant. *We predict that tolcapone, relative to placebo and to baseline, will reduce ALC vs. BEV activation of OFC and vmPFC and reduce dmPFC, dIPFC, and IFG activation for the successful vs. unsuccessful inhibitions and post-error slowing contrasts. Further, we predict that these effects will be greatest among val-allele homozygotes, that they will be related to drinking, and that they will mediate the medication by genotype interaction on drinking.*

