## C. PROTECTION OF HUMAN SUBJECTS

### 1) Risks to Human Subjects

#### a) Human Subjects Involvement, Characteristics, and Design

We anticipate that the ARC Clinical Intake and Assessment Core (CIAC) will refer 90 subjects to us for participation. Half of these subjects will be randomized to tolcapone, and the other half to placebo medication. We anticipate that 70% of subjects will be male and 30% female, and that approximately 20% of subjects will be racial and ethnic minorities. No special vulnerable populations will be involved in this research.

During assessment at the CIAC, subjects will receive liver function tests, and those with normal liver enzymes (transaminases) will be genotyped for the COMT val158met single nucleotide polymorphism (SNP). Due to the allele frequencies for this SNP, all subjects with the met/met genotype will be referred for participation, as will approximately half of the subjects with the val/met genotype and two-thirds of the subjects with the val/val genotype. Subjects with normal liver enzymes who have the val/met or val/val genotype will be randomly chosen for referral to this study or to the other clinical component of the ARC or an ARC pilot study.

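### Aim 2 power: 90 subjects with d = 0.5 on both arms of the indirect effect give about 0.39 by joint significance (0.19 to 0.51 across tests), not 0.8, so either the power figure or the effect-size label is wrong

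*Combined protocol and SAP*

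**What the plan says.** The combined protocol and SAP, section B.5)b) (Sample size determination and power analysis), gives the Aim 2 calculation in one sentence. It opens "For 90 subjects and medium effect sizes", labels the effect d = 0.5, and ends "for the two arms of the indirect effect, power to detect a mediated effect is 0.8". The same paragraph says that "mediation will be determined by the significance of the joint" product of the *a* and *b* paths. It takes its power figure from a published source whose authors "have conducted large-scale simulation to form empirical estimates of power for mediated effects". That source's table is not reproduced. The section closes by stating that "power analyses for both Aims 1 and 2 suggest that a total" sample of 90 gives power of at least 0.8.

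For Aim 2 the section states no alpha, no sidedness, no specific test of the product (Sobel, joint significance or bootstrap), and no rule for turning *d* into a path coefficient. Allocation is given in section C.1)a): "Half of these subjects will be randomized to tolcapone, and the other half to placebo medication".

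**The concern.** A two-group comparison with 45 per arm at d = 0.5 is well known to fall short of 0.8 power. A mediated effect needs two links to be detected, so its power should be lower than that of a single link, not higher. A claim of 0.8 with d = 0.5 on both links therefore looked impossible on its face.

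The figure is one of two stated supports for N = 90. If it is wrong, a reader cannot tell whether Aim 2 was planned for d = 0.5 with power somewhere between 0.2 and 0.5, or for a clearly larger effect with power 0.8. That matters for interpreting a null mediation result.

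**Working it through.** **Inputs from the document.** N = 90; d = 0.5 on each arm; stated power 0.8; test based on the *a\*b* product (all section B.5)b)); equal allocation, so 90 / 2 = 45 per arm (section C.1)a)).

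**Assumptions, because the document is silent.** Two-sided alpha 0.05, with one-sided 0.05 as a variant; all 90 subjects analysed; a simple medication → activation → drinking model with no direct effect; *d* converted by r = d / √(d² + 4) = 0.5 / √4.25 = 0.2425.

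**Step 1: path *a* alone.** This step needs no conversion to *r*. The noncentrality is d·√(n/2) = 0.5 × √22.5 = 2.37. The t-test power is 0.650 two-sided and 0.761 one-sided. Joint significance requires path *a* and path *b* together, so it cannot exceed 0.65 (two-sided), whatever path *b* is.

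**Step 2: the mediated effect with d = 0.5 on both paths.** Simulation with balanced binary X, M = rX + e, Y = rM + e, variables standardised, N = 90, two-sided 0.05 (40,000 runs; bootstraps 2,500 runs × 1,000 resamples):

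| Quantity | Power |
|---|---|
| Path *a* | 0.65 |
| Path *b* given X | 0.61 |
| Sobel | 0.19 |
| Joint significance | 0.39 |
| Percentile bootstrap | 0.39 |
| Bias-corrected bootstrap | 0.51 |

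As a rough check, 0.649 × 0.609 = 0.395, in line with the joint result. An independent simulation that varied the scaling (path 0.243 or 0.25, continuous or binary X) gave joint 0.37 to 0.41, Sobel 0.17 to 0.20, percentile bootstrap 0.36 to 0.41 and bias-corrected bootstrap 0.48 to 0.53. The stated 0.8 is not reproduced.

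**Step 3: more generous readings.**

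- One-sided 0.05, d = 0.5 on both paths: joint 0.55, Sobel 0.38, bias-corrected bootstrap about 0.66.
- d = 0.5 kept for path *a* only, path *b* raised to a standardised 0.5 to 0.9, two-sided: joint 0.64 to 0.65, Sobel 0.59 to 0.66, percentile bootstrap 0.66 to 0.69, bias-corrected bootstrap 0.66 to 0.71.
- The same mixed reading with path *b* at 0.5, one-sided, bias-corrected bootstrap: 0.81. This reaches 0.8 but does not put d = 0.5 on both arms, and nothing in the text supports it.
- 0.5 read as a standardised path coefficient on both arms: 0.98 or higher on every test, so this does not match 0.8 either.

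**Step 4: what would give 0.8 at N = 90.** With equal paths, and d = 2r / √(1 − r²):

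| Test | r on each path | Power there | d |
|---|---|---|---|
| Bias-corrected bootstrap | 0.315 | 0.803 | 0.63 / 0.949 = 0.66 |
| Joint significance | 0.34 | 0.809 | 0.68 / 0.940 = 0.72 |
| Sobel | 0.37 | 0.789 | 0.74 / 0.929 = 0.80 |

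An assumed regression coefficient of 0.39 on both paths (not in the documents) gives Sobel power of 0.80 to 0.86 depending on scaling, so it can reproduce the stated figure.

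**Step 5: N needed if d = 0.5 is right.** Power reaches 0.8 at about N = 174 by joint significance (0.799) and about N = 218 by Sobel (0.801).

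**The case against.** The strongest reply is that d = 0.5 is a slip of notation and the power is sound. The paragraph calls the effect medium, speaks of path coefficients and cites a source described as working on a regression effect-size scale. Path *b* links two continuous variables, so a two-group *d* is not its natural measure, and the conversion to *r* is supplied here, not by the plan. A coefficient near 0.39 returns 0.80 by Sobel. This may well be what happened, and for that reason the result should not be read as proof that Aim 2 has 39% power. But the intended coefficient cannot be confirmed from the documents. If this reading is right, the printed effect size is still wrong, and only the correction differs.

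A second reply is that joint significance is not strictly the product test named in the power paragraph. That is fair, so the product tests are shown alongside; none reaches 0.8. Joint significance is also close to what section B.5)e)4 asks for, since complete mediation there requires both links to be significant.

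A third reply is that N = 90 has separate support from Aim 1 and the remedy changes no analysis. That is true and limits the consequence, but the plan explicitly rests its conclusion on both aims.

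**Conclusion.** The concern holds. With d = 0.5 on both arms and 90 subjects, no test examined, one-sided or two-sided, gives 0.8. Two-sided power is 0.19 to 0.51, with 0.39 by joint significance; the best one-sided result is about two-thirds. Either the power or the label is wrong, and the documents do not say which. The conclusion that 90 subjects give at least 0.8 power is unsupported for Aim 2 as written.

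The exact figures depend on the assumed alpha, the conversion from *d* and the single-mediator model. The cap of 0.65 from path *a* on two-sided joint significance depends only on alpha, the 45/45 split and d = 0.5.

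**What to change.** Restate the Aim 2 sentence with the path coefficients, the test of *a\*b* and alpha, in one of two ways.

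1. **If d = 0.5 was meant:** for 90 subjects (45 per arm), two-sided alpha 0.05 and d = 0.5 (r = 0.24) on each arm, give power of about 0.39 by joint significance, or the matching figure from step 2 if another test is chosen. Then remove Aim 2 from the conclusion that N = 90 gives at least 0.8 power.
2. **If a larger regression-scale effect was meant:** replace d = 0.5 with that coefficient, name the test, and keep 0.8 only if that test delivers it (about r = 0.34 for joint significance, r = 0.37 for Sobel).

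In either case, add that the figure is for a simple medication–activation–drinking path with every scan usable. Section B.5)e)4 instead tests "individual mediators of the medication by genotype interaction on drinking", and under section B.5)e)1 subjects beyond the stated limit for translational or "rotational movement during either task will be excluded from analysis". This note is not needed for the correction itself.

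The cost is wording only, with no change to N or to the analyses. The downside is that either the stated Aim 2 power or the stated detectable effect becomes less favourable.
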